# Comparative Evaluation of Post-operative pain with different apical finishing sizes after single visit root canal treatment

## Introduction:

Apical preparation size is a very important variable in the process of root canal preparation. There have been many conflicts regarding the proper size and how it affects bacterial reduction, root canal dentine strength in terms of conservation and even post-operative pain. Post-operative pain as a patient related outcome, with different apical sizes is very important. In this study, we will evaluate the postoperative pain after root canal enlargement with two sizes after the binding file compared to three sizes after the binding file without disregard of mechanical principles of root canal preparation.

## Materials

E3 Azure Poldent files

Resin sealer

k-files Mani

## Subjects:

This is a proposed randomized controlled parallel clinical, prospective split mouth, triple blinded study. Sample size calculation was conducted using G\*Power 3.1.9.4 software based on data obtained from a previous study.[[name]'s paper which compared the effect of different kinematics on post operative pain(patients) ] It was estimated that a minimum sample size of 19 subjects (sides) per group for a total of 38 sides would be essential for an effect size of 0.97 with an alpha error of 0.05 and a power beta of 0.90 to achieve 95% confidence of a true difference between the groups. Sample size was increased by 25% to 25 subjects per group for a total of 50 sides to compensate for drop-outs.

## Inclusion criteria:

Of the 25 patients all must have the following:

Age: 20-50

Gender: Males and Females, random selection.

Systemic status: healthy patients (Category: American Society of Anaesthesiologists class 1)

Bilateral exposed mandibular first or second permanent molars

Molars should have separate mesial and distal roots

Mesial roots confirmed to be type three root canal system

Distal root confirmed to be type one root canal system

Normal periapical radiograph and no bone changes

Symptomatic irreversible pulpitis

I.B.F. in mesial roots not more than #20, and distal root not more than #30

#### Exclusion criteria:

Type two root canal system in mesial roots

Type two or three root canal systems in distal roots

Signs of apical involvement in the radiograph

Any systemic conditions altering the treatment or requiring medications or precautions

#### Patient selection and preparation:

All root canal treatments were performed by a single endodontic consultant. All subjects were selected from walk in patients presented to the endodontic clinic of the British university in Egypt. Cases that were diagnosed and did not meet the inclusion criteria were referred to the intern clinic for dental care. Cases that met the inclusion criteria were selected for this study. All patients were verbally informed about the procedure's benefits and that the results of the treatment will be used to this study and the risks of the procedure was explicitly explained to them. After the verbal consent patients were handed a written form consent to sign upon.

#### Procedure:

Radiographs were taken by a Paralleled long cone periapical radiography. To ensure a visible root canal  $\leq 30^\circ$  of canal curvature and a periapical index (PAI score) of 3–5 according to Orstavik et

al., (1986) in addition of initial confirmation of root canal types. All patients were anesthetized, rubber dam applied, and access cavities were performed. After root canal exploration and scouting, root canal systems were reconfirmed to be the types selected for this study.

Initial binding file was selected for all root canals to ensure it met the inclusion size of mesial roots #20 and distal #30. After patency and glide path were performed by K-files up to size #20, engine driven canal enlargement was applied using E3 Azure files to final finishing size according to the grouping.

Group A: (left side of the patient) will be prepared 2 sizes larger than the IBF, to size 35#/.04 mesial canals and 40#/.04 distal canals.

Group B: (right side of the patient) will be prepared 3 sizes larger than the IBF, to size 40#/.04 mesial canals and 45#/.04 distal canals.

All data of post-operative pain will be recorded by a second blinded clinician through a visual analog scale (VAS). Post-operative monitoring periods will be recorded in 12 hours, 24 hours, 3 days and 1 week.

Data will be sent to the statistician with group names only to fulfill the triple blinding criteria and results will be interpreted

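### The Procedure section screens for a PAI score of 3–5, while the eligibility lists require a normal periapical radiograph

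*Protocol*

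**What the plan says.** Three places in the protocol set a rule on periapical status as seen on the radiograph.

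- **Inclusion criteria:** the list is binding on every one of the 25 patients and contains "Normal periapical radiograph and no bone changes".
- **Exclusion criteria:** the list contains "Signs of apical involvement in the radiograph".
- **Procedure:** periapical radiographs are taken to ensure a limit "of canal curvature and a periapical index (PAI score) of 3–5". The index is attributed to a cited source, and its score meanings are not printed.

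Two further statements bear on which rule was used. Patient selection and preparation says "Cases that were diagnosed and did not meet the inclusion criteria were referred to the intern clinic for dental care" and "Cases that met the inclusion criteria were selected for this study". The Procedure section, for its part, continues its radiograph sentence with "in addition of initial confirmation of root canal types" and then checks the initial binding file "to ensure it met the inclusion size of mesial roots #20 and distal #30". The PAI appears in neither criteria list.

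**The concern.** The lists describe teeth with irreversible pulpitis and no radiographic periapical change. If PAI 3–5 denotes periapical change, the Procedure section describes teeth that the lists rule out. These are different populations for a trial whose outcome is post-operative pain, and a reader of the protocol cannot tell which was studied.

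The Procedure sentence cannot be set aside as mere narrative. It is worded as a requirement, and its neighbours verify listed criteria: canal type ("Mesial roots confirmed to be type three root canal system" is an inclusion criterion) and binding-file size. It therefore reads as the step at which eligibility is confirmed, against a radiographic rule that the lists do not contain.

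**Working it through.** This is a consistency check, and the plan gives no figure of its own to reproduce.

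**Inputs**

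- Listed rule: normal radiograph, no bone changes, no apical signs (Inclusion and Exclusion criteria).
- Procedure rule: PAI in {3, 4, 5}, that is, 3 grades (Procedure).
- Planned size: 25 patients × 2 sides = 50 sides (Subjects; Inclusion criteria).
- Meaning of the scores: not given in the protocol. Assumption: grades run from 1 to 5, low scores are normal and higher scores show periapical change. Alternatives are shown below.

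**Step 1: overlap of the two rules.** For each possible set N of grades that count as normal, take the intersection of N with {3, 4, 5}.

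| Reading of the scale | N | Overlap with {3, 4, 5} | Consequence |
|---|---|---|---|
| Low = normal | {1} | none (0 of 3) | No tooth meets all three statements |
| Low = normal | {1, 2} | none (0 of 3) | No tooth meets all three statements |
| Low = normal, generous | {1, 2, 3} | {3} (1 of 3) | Grades 4 and 5 still conflict |
| Reversed, high = normal | {5} | {5} (1 of 3) | Can be met together; Procedure rule is looser |
| Reversed, high = normal | {4, 5} | {4, 5} (2 of 3) | Can be met together; Procedure rule is looser |

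Under the assumed direction, with N = {1} or {1, 2}, the contradiction is complete. In the other three rows a tooth could satisfy every statement, but the Procedure range still admits at least one grade outside N. The two rules would coincide only if grades 3, 4 and 5, and no others, all meant normal with no bone changes. Nothing in the protocol supports that.

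**Step 2: bounds on the sides affected**, under the assumed direction with N = {1} or {1, 2}.

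- Lists govern: 0 of 50 sides fall outside the listed criteria.
- Every side held to PAI 3–5: 50 of 50 fall outside them.
- All three statements enforced together: no tooth is eligible.

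The document does not allow the true number to be placed between 0 and 50, and it gives nothing from which an effect on pain scores could be calculated.

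**The case against.** The strongest reply has three parts.

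First, the decisive premise lies outside the protocol: the score meanings are not printed, and under a reversed scale the statements could be met together. This stands as a limit on the strong form of the claim, that no tooth qualifies. It does not remove the mismatch, because the two rules still differ in every reading tabulated.

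Second, the protocol read as a whole points towards the lists. They bind every patient, the exclusion list repeats the point, and patients who failed the inclusion criteria were sent elsewhere. Against this stands one grammatically incomplete sentence. This also largely stands: the range is probably a drafting error. But no precedence is stated, and that sentence sits in the text where other criteria are verified.

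Third, on that favoured reading nobody is wrongly enrolled and neither the estimate nor the power changes, and a range of 0 to 50 of 50 spans every possible value. This is fair: the figures are logical bounds, and the upper one should not be read as a likely outcome. The matter still needs correcting, because the section on patient selection and much of the Procedure section are in the past tense. Screening may already have taken place under either rule, and the protocol cannot show which.

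**Conclusion.** The concern holds. The protocol states its radiographic eligibility rule in two ways that do not agree. On the assumption that low PAI scores are normal, with score 3 and above showing periapical change, no tooth can satisfy the Inclusion criteria, the Exclusion criteria and the Procedure section together. That conclusion depends on the assumed direction of the scale and on where normal ends; the lack of reconciliation between the sections does not.

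If the lists governed, the intended population is enrolled and the fault is confined to a Procedure section that misdescribes it. If the Procedure range was followed, teeth that the lists rule out entered the trial. The size is known only as 0 to 50 of 50 sides, and no bias in pain scores is shown. It should be treated as a required correction, because an eligibility threshold that would admit what the criteria exclude is wrong as written.

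**What to change.** The sponsor should confirm which radiographic criterion was intended and state that one criterion identically in the Inclusion criteria, the Exclusion criteria and the Procedure section. If a PAI range is kept, the meaning of each score should be printed so that the range can be checked against the wording of the lists. This review does not say which criterion is right.

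The cost is a short text correction. If patients have already been screened, the sponsor should also establish which rule was applied by re-reading the radiographs already taken, at most 50 sides if the planned number is enrolled. No additional patients or procedures are needed.

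### Final eligibility (IBF size and canal type) is judged after access by an operator who already knows the arm from the side of the mouth

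*Protocol*

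**What the plan says.** Under Inclusion criteria the Protocol sets anatomical conditions: "Mesial roots confirmed to be type three root canal system", "Distal root confirmed to be type one root canal system", and "I.B.F. in mesial roots not more than #20, and distal root not more than #30".

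The Procedure section gives the order of events. Periapical radiographs provide a first confirmation of canal type. Then "All patients were anesthetized, rubber dam applied, and access cavities were performed". Next, "After root canal exploration and scouting, root canal systems were reconfirmed to be the types selected for this study", and "Initial binding file was selected for all root canals to ensure it met the inclusion size of mesial roots #20 and distal #30". Enlargement to the finishing size of the group follows.

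Allocation is by anatomy: "Group A: (left side of the patient) will be prepared 2 sizes larger than the IBF", and the right side is Group B, prepared three sizes larger. Under Patient selection and preparation, one consultant performs all the treatments. The same section deals with ineligible cases in one sentence: "Cases that were diagnosed and did not meet the inclusion criteria were referred to the intern clinic for dental care". The masking in the Procedure section concerns the clinician who records the VAS and the statistician.

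**The concern.** A comparison of two arms needs the decision to keep a unit to be independent of its arm. Here the last eligibility decision comes after the arm is known, and the person making it is about to deliver the treatment. If a borderline canal is judged more strictly on the side due for one finishing size than on the other, the retained left and right sides no longer have comparable anatomy. IBF is a sensitive variable for this to happen on. The groups are defined relative to it and also have stated finishing sizes, so it bears on how far a canal is enlarged. A difference in pain between arms could then partly reflect which canals were let in.

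An analysis plan cannot repair this. The order of eligibility, allocation and treatment is fixed by the protocol, and concealment cannot be restored once a side has been judged with its arm known.

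**Working it through.** No arithmetic settles this point; it turns on the order of events and on who knows what at each step.

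1. **What decides eligibility.** Mesial canal type, distal canal type and IBF limits (Inclusion criteria).
2. **When each is settled.** Canal type is provisional on the radiograph and final after access. IBF needs a file in the canal, so its first and only measurement comes after anaesthesia, rubber dam and access (Procedure).
3. **Who decides.** One consultant does all treatments (Patient selection and preparation), and the protocol names nobody else for these checks.
4. **What that person knows.** Left means Group A and right means Group B (Procedure), so the arm is known before the tooth is opened, in every patient.
5. **Whether masking covers it.** The masking described applies to pain recording and analysis. The operator has to know the finishing size to prepare the canal, and nothing withholds it until eligibility is settled.
6. **What happens to a failure at this stage.** The referral sentence is worded for cases failing at diagnosis. The protocol does not say how a failure after access is handled or recorded, or whether both molars must pass before either is enlarged.

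Steps 2 to 5 together mean that eligibility is finally judged with the arm known and without a safeguard.

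**Does removing the whole patient when one side fails cure this?** No. Suppose the IBF limit is applied more strictly on the right. Patients with a borderline right canal leave with both sides, but those who remain have been selected on the right canal and not equally on the left. The wide end of the IBF distribution is cut harder in Group B than in Group A. Only a limit applied alike to both sides avoids this, and concealment is what protects that.

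**Size.** A figure would need the share of canals near the limit, the difference in strictness between sides, and the relation between IBF and VAS pain. The documents give none of these, so no figure is offered.

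**The case against.** Several points against the concern are sound, and they limit how far it goes.

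- **Loss of sample size.** A reader might infer that failures at access eat into the margin from 25 patients to the required 19. With an assumed failure probability p per molar, independent between sides, 25 × (1 − p)² pairs would remain: 22.6 at 5%, 20.3 at 10%, 18.1 at 15% and 16.0 at 20%. The margin would be gone at p = 1 − √(19/25) = 0.128. The documents do not support this use of the formula. The Inclusion criteria are required of all 25 patients, so a patient who fails at access is a screen failure and not a loss from the 25. They also give no p, and two molars in one mouth need not be independent.
- **Treatment in sequence.** A reader might infer that one molar is treated before the other is checked, leaving an unpaired side. The text does not say so. It speaks of access cavities in the plural and of IBF for all canals before enlargement, which can mean that both teeth are gauged first. The order of the sides and the number of visits are simply not stated.
- **Canal type.** It would be too strong to say that all three criteria can be settled only after access. The radiograph screens canal type beforehand, which should reduce late failures. The IBF has no such earlier check, and it sustains the point alone.
- **Narrow canals.** The IBF criterion has upper limits only. A tight canal passes it, so only a wide canal can be excluded on IBF.
- **Overlap with the allocation rule.** The operator knows the arm because sides are not randomised, so one can argue that this belongs to that defect. In part it does. But randomising sides would not help if the allocation were disclosed before the IBF is gauged; the timing needs its own sentence.

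**Conclusion.** The point holds in this form: IBF eligibility is first judged, and canal-type eligibility finally judged, after access by an operator who knows the arm. The protocol contains no safeguard against selective exclusion. The possible consequence is a difference in anatomy between the retained left and right sides, of a size that cannot be derived from the documents.

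This describes an open path. It does not show that any side was excluded improperly, that pairs were broken, or that the study falls short of 19 pairs. The conclusion rests on two readings: that the consultant who treats is also the person who gauges the canals, and that the left/right rule is applied as written. The change is worth making because it is cheap and cannot be made afterwards.

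**What to change.** In the Procedure section:

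1. Replace the fixed left/right rule with a concealed random allocation of sides, for example in sealed envelopes. Without this the rest cannot work, since the side itself reveals the arm.
2. Open the allocation only after canal type and IBF have been recorded for every canal. Where both molars are treated in one session, record both before opening it.
3. State explicitly that a patient counts among the 25 only when both molars have qualified, as the Inclusion criteria already imply.
4. Log every post-access failure by side, arm and reason. Someone other than the operator can supply the arm where the allocation is still unopened.
5. Reconcile the referral sentence, which is worded for failures at diagnosis, with failures found after access. How those patients are managed is for the investigators to decide.

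**Cost.** An allocation list with concealment, a short log and a change of sequence; no additional clinical procedure. One limit remains: if the sides are treated on different days, the second side's arm is known by elimination. Failures on the second side must then be reported by arm so that a reader can judge whether they are balanced.

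### The trial is called randomised, but every left molar is Group A and every right molar is Group B, so apical size cannot be separated from side

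*Protocol*

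**What the plan says.** The Subjects section of the protocol describes the design as follows: "This is a proposed randomized controlled parallel clinical, prospective split mouth, triple blinded study". The Procedure section then assigns the groups by side of the mouth, without exception: "Group A: (left side of the patient) will be prepared 2 sizes larger than the IBF" and "Group B: (right side of the patient) will be prepared 3 sizes larger than the IBF".

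The protocol describes no random sequence, list, envelope or other chance element for allocation. The only other mention of randomness is in the Inclusion criteria, "Gender: Males and Females, random selection", which concerns the sex of patients and not the assignment of teeth.

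Two further statements bear on the point. Under Patient selection and preparation: "All root canal treatments were performed by a single endodontic consultant". At the end of Procedure: "Data will be sent to the statistician with group names only to fulfill the triple blinding criteria". That section also says that a second, blinded clinician records the pain scores.

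**The concern.** Randomisation supports reading a difference in pain as an effect of apical size. In a split-mouth trial, pairing removes differences between patients but not differences between the two sides. Only random assignment of side to treatment balances those, and the Procedure section replaces it with a constant rule.

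A systematic left-right difference would be counted as an effect of apical size. One possible source is the single operator, whose access or handling may differ between sides. Another is treatment order, if order follows side. The protocol states neither, so both are assumptions. Differences between a patient's two teeth that do not run consistently left to right only add noise.

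Blinding is also weakened, though nothing in the protocol shows that it is broken. A pain recorder who knows which side a score refers to, and knows the rule, knows the group. The group names sent to the statistician are labels that the protocol itself defines by side.

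**Working it through.** **The protocol's own figure.** The Subjects section gives an effect size of 0.97, alpha 0.05, power 0.90 and a minimum of 19 sides per group. A one-sided t-test for independent samples needs 18.92, rounded up to 19, so the figure reproduces on that basis. Adding 25% gives 19 × 1.25 = 23.75, close to the stated 25 per group (25 patients × 2 sides = 50 sides). These numbers do not bear on the allocation problem. They only supply the 19 and 25 pairs used below.

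**Allocation as written.** Inclusion requires molars on both sides, one for each group. Under the Procedure section:

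- P(Group A | left) = 1 and P(Group B | left) = 0.
- P(Group A | right) = 0 and P(Group B | right) = 1.

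Any random within-patient assignment would put these probabilities strictly between 0 and 1.

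**What the paired contrast estimates.** Let τ be the effect of size (A minus B), λ the systematic left-minus-right difference, and e the within-patient error. For patient i:

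- Fixed sides: D_i = τ + λ + e_i, so the mean of D estimates τ + λ. Since λ has the same coefficient as τ in every patient, the two cannot be separated at any sample size.
- Side randomised within patient: D_i = τ + S_i λ + e_i, with S_i = +1 or −1 with equal probability. S_i averages to zero, so the mean of D estimates τ.

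**Illustration of size.** The protocol gives no value for λ, so a range is assumed. Set τ = 0 and let δ = λ / SD(e) be 0.1, 0.2, 0.3 or 0.5. Also assume a two-sided 5% paired t-test, since the protocol names no test. With n pairs, the rejection probability under fixed sides is

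P(|T| > t(0.975, n−1)), where T is noncentral t with n−1 degrees of freedom and noncentrality δ√n.

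For n = 25, √n = 5, so the noncentrality is 0.5, 1.0, 1.5 or 2.5. The rates under randomised side come from 200,000 simulated trials per setting.

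| Assumed δ | 0.1 | 0.2 | 0.3 | 0.5 |
|---|---|---|---|---|
| Fixed sides, 25 pairs | 7.7% | 16.1% | 30.2% | 67.0% |
| Fixed sides, 19 pairs | 7.0% | 13.1% | 23.6% | 54.1% |
| Simple randomisation of side, 25 pairs | 5.0% | 5.1% | 4.9% | 5.0% |
| Simple randomisation of side, 19 pairs | 4.9% | 5.0% | 5.0% | 5.0% |
| Balanced randomisation, side not modelled, 25 pairs | 4.9% | 4.7% | 4.0% | 3.0% |
| Balanced randomisation, side not modelled, 19 pairs | 4.8% | 4.5% | 4.1% | 3.1% |

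Under balanced randomisation the rate falls below 5% because the side difference inflates the SD of D without shifting its mean.

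**More patients do not help.** At δ = 0.2 the false-positive rate under fixed sides rises from 16.1% with 25 pairs to 28% with 50 and 51% with 100, because the noncentrality grows with √n.

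**The case against.** The strongest reply is that harm needs a systematic left-right difference in pain, and the protocol neither gives nor suggests one. Split-mouth pairing already balances patient-level factors, and a single operator removes differences between operators. At 0.1 SD the error rate is 7.7%, a modest departure from 5%, and the 67.0% needs a 0.5 SD difference with nothing to anchor it. The test behind the percentages is also assumed, because the protocol names no test. All of this stands, so the percentages are an illustration and carry no weight for severity. They also show only one direction: a side difference opposite in sign to a real size effect would hide it.

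It can further be said that some contributors to a side difference, such as treatment order or first versus second molar, could be adjusted for if they are recorded and vary across patients. That is correct, but it leaves the side effect that remains inseparable from size. The blinding point is conditional on who knows the rule and is secondary.

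None of this touches the core. The protocol claims randomisation and then states a deterministic rule. A statistical analysis plan could describe how a random list is made, but it could not make fixed sides random.

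**Conclusion.** The concern holds and must be fixed. The design label in the Subjects section is contradicted by the allocation rule in the Procedure section, and the effect of apical size is not identifiable separately from side. Both conclusions follow from the text alone and need no assumed side effect.

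The practical size is unknown. It depends on a left-right difference that the protocol does not give and, for the rates shown, on a two-sided paired t-test with normally distributed differences. A side difference of zero would do no harm, but this trial has no way to show that it is zero.

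**What to change.** **If treatment has not started.** In the Procedure section, replace the fixed left and right sides with a concealed random assignment for each patient: left A and right B, or left B and right A. Reveal it to the operator only after enrolment and as late as practicable before final enlargement of the first treated tooth. State that a second tooth later found ineligible does not change the assignment. If the two teeth are treated in sequence, state how the order is decided, keep it from being determined by group, and record it. Keep the side-to-group key from the pain recorder, and send the statistician neutral codes.

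The cost is a short protocol change, a 25-line list and sealed envelopes. Someone other than the operator, the pain recorder and the statistician has to prepare and hold the list. Sample size, visits and the two preparation sizes do not change.

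**If treatment has already been given by fixed side.** The past tense in parts of the protocol may suggest this, although the Subjects section still calls the study proposed. In that case, remove the word randomised, qualify the claim of triple blinding, and report the confounding of size with side as a limitation. This changes only the wording; the confounding itself cannot be repaired.

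### Each arm is defined by two rules, a number of sizes above the initial binding file and a fixed finishing size, that cannot both hold for the canals the protocol admits

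*Protocol*

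**What the plan says.** The Introduction gives the aim in relative terms only: "two sizes after the binding file compared to three sizes after the binding file".

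The Procedure section then describes each arm in one sentence that carries two rules. Group A, the left side, "will be prepared 2 sizes larger than the IBF, to size 35#/.04 mesial canals and 40#/.04 distal canals". Group B, the right side, "will be prepared 3 sizes larger than the IBF, to size 40#/.04 mesial canals and 45#/.04 distal canals".

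Eligibility limits the IBF from above only: "I.B.F. in mesial roots not more than #20, and distal root not more than #30". The Procedure repeats the check without the words of limit: "Initial binding file was selected for all root canals to ensure it met the inclusion size of mesial roots #20 and distal #30".

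The Materials section lists "E3 Azure Poldent files" without sizes, so the series on which sizes are to be counted is not printed. No sentence says which rule applies when the two differ.

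**The concern.** A fixed finish can be two or three sizes above the IBF only for particular starting sizes, and the protocol admits a range of them. Apical finishing size is the only intended treatment difference in this split-mouth trial, so its definition fixes what the pain comparison means.

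If the fixed sizes are followed, the enlargement beyond the IBF varies from canal to canal and need not be +2 versus +3. If the relative rule is followed, some of the printed sizes are wrong. Either way a pain result could be reported against a question that the treatment given did not test.

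**Working it through.** **Inputs.** Procedure: relative rule A = IBF +2, B = IBF +3; fixed sizes A #35 mesial and #40 distal, B #40 mesial and #45 distal. Inclusion criteria: mesial IBF at most #20, distal IBF at most #30.

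**Step 1: a check that needs no particular file series.** An IBF of #20 is eligible mesially (20 ≤ 20) and distally (20 ≤ 30). Apply both rules from #20:

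- mesial canal, arm B: the finish is #40, so #40 must be three sizes above #20;
- distal canal, arm A: the finish is #40, so #40 must be two sizes above #20.

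The number of sizes from #20 to #40 is one number on any one series. It cannot be both 3 and 2. The only assumption is that the same series is used for both roots, and the protocol suggests nothing else.

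**Step 2: size of the mismatch on steps of 5.** This series (10, 15, 20, ..., 45) is an assumption. It fits the distal ceiling: (40 − 30)/5 = 2 and (45 − 30)/5 = 3. Sizes above the IBF = (fixed finish − IBF)/5.

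| Root | IBF | Fixed sizes amount to (A/B) | IBF rule would give (A/B) | Printed (A/B) |
|---|---|---|---|---|
| Mesial | #20 | +3/+4 | #30/#35 | #35/#40 |
| Mesial | #15 | +4/+5 | #25/#30 | #35/#40 |
| Mesial | #10 | +5/+6 | #20/#25 | #35/#40 |
| Distal | #30 | +2/+3 | #40/#45 | #40/#45 |
| Distal | #25 | +3/+4 | #35/#40 | #40/#45 |
| Distal | #20 | +4/+5 | #30/#35 | #40/#45 |

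Mesially, +2/+3 needs an IBF of 35 − 2 × 5 = #25, which the inclusion criteria exclude. Distally the rules agree only at #30.

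**Step 3: sensitivity to the series.**

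- Without #25: mesial #20 gives +2/+3 and agrees, #15 gives +3/+4 and #10 gives +4/+5; distal #30 gives +2/+3 and #20 gives +3/+4.
- Counting only on files 30, 35, 40, 45 (hypothetical): every mesial IBF up to #20 gives +2/+3 and agrees; distal #30 gives +2/+3, but #25 and #20 give +3/+4.

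The mesial conflict therefore depends on the series. On each of the three series tried, some eligible canals conflict, as Step 1 requires.

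**Step 4: the contrast between arms.** The fixed sizes differ by 40 − 35 = 5 mesially and 45 − 40 = 5 distally, one step. The relative rule also differs by one size (3 − 2) when both sides have the same IBF. When they differ (steps of 5, mesial), left #20 and right #15 both finish at #30; left #20 and right #10 finish at #30 (A) and #25 (B), which reverses the order.

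**The case against.** The best defence is that the fixed sizes plainly govern. The title speaks of "different apical finishing sizes", the group sentences print one exact size and taper per root and arm, and one consultant treats everyone, so operators cannot differ in their reading. On this view the relative wording is loose description. That is a fair guess at the intention, and it is why keeping the fixed sizes is the preferred fix. It does not remove the contradiction, because the Introduction states the aim only in relative terms.

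A second defence reads the Procedure's check as exact sizes, mesial #20 and distal #30. The distal figures then agree, and the mesial ones agree only on a series with a single size between #20 and #35. But the inclusion criterion sets an upper limit, so smaller IBFs are eligible.

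Three stronger readings are tempting, and the document does not support them:

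- A reader might infer that a #35 mesial finish could belong to either arm. It could not: the arm is set by side, left A and right B. Only the label +2 or +3 is uncertain.
- A reader might take the mesial +3/+4 as established. It rests on steps of 5, which are not printed.
- A reader might conclude that, on any series, at most one IBF per root can satisfy both rules. That fails if IBFs need not belong to the counted series, as the 30-to-45 example shows for mesial canals.

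**Conclusion.** Wrong as written. The two rules in the Procedure cannot both hold for all the canals that the inclusion criteria admit, whatever file series is used for both roots.

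On steps of 5 the discrepancy is at least one size in every eligible mesial canal, as large as the difference between the arms, and it arises distally at every IBF below #30. The protocol gives no distribution of IBFs, so the share of canals affected distally, or at each size, cannot be stated.

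The harm is limited. Arm membership is clear and the contrast between arms stays about one size. What fails is the match between the stated question, +2 versus +3, and the comparison that the fixed sizes deliver.

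**What to change.** **Preferred: keep the fixed sizes.** In the Procedure, delete the relative clause from both group sentences, so that Group A finishes at #35/.04 mesially and #40/.04 distally, and Group B at #40/.04 and #45/.04. In the Introduction, restate the aim as a comparison of those two sets of sizes. The title already fits. The cost is an edit to two sentences in the Procedure and one in the Introduction. Printed sizes, eligibility, patient numbers and visits do not change.

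**If the investigator intends the IBF rule instead.** Delete the fixed sizes, name the file series, and say how patients whose left and right IBFs differ are handled, because their two finishes can coincide or reverse. This is more than an edit of wording: on steps of 5 the mesial finishes from IBF #20 become #30/#35 instead of #35/#40, which needs clinical confirmation. At IBF #10, arm A would end at #20, the size named for the hand-file stage ("After patency and glide path were performed by K-files up to size #20"), so the investigator should say whether that is intended.

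Raising the mesial ceiling to #25, which the printed mesial sizes fit on steps of 5, would not be enough: #20 would still be eligible in both roots and the contradiction in Step 1 would remain.

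**If patients have already been treated**, as the partly past-tense text may suggest, report the rule actually followed and describe the comparison in those terms.
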